3.1.1 Screening Phase

All patients will undergo screening assessments within 28 days prior to the first dose of rucaparib. AEs that occur after signing of the informed consent form and before administration of the first rucaparib dose will also be collected during this period.

Screening assessments will include demographics and medical history, prior treatments for pancreatic cancer (and other malignancies if applicable), prior and current medications and procedures, 12-lead electrocardiogram (ECG), ECOG performance status, hematology, serum chemistry, serum pregnancy for women of childbearing potential, urinalysis, physical examination, vital signs, weight and height measurements, adverse events, and radiological assessment by CT or magnetic resonance imaging (MRI). An optional tumor biopsy sample will be collected from patients who provide appropriate consent.

BRCA1/2 or PALB2 test results must be obtained for all patients prior to enrollment in order to confirm the mutation detected was classified as deleterious/pathogenic or suspected deleterious, or equivalent of either of these. *BRCA1/2 or PALB2* mutations in blood and tumor tissue samples may be collected for confirmatory analysis.

All patients who enroll on study must have a confirmed, deleterious/pathogenic or suspected deleterious or equivalent mutation in BRCA1, BRCA2 or PALB2. Mutations may be germline or somatic in origin and must have been identified by a CLIA certified laboratory from any of the following: blood, tumor tissue or circulating tumor material.

CONFIDENTIAL

This material is the property of the University of Pennsylvania.

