4.1 Inclusion Criteria

Eligible patients must meet the following inclusion criteria:

- Histologically or cytologically confirmed diagnosis of pancreatic carcinoma with locally advanced or metastatic disease
- ≥ 18 years of age.
- Eastern Cooperative Oncology (ECOG) performance status of 0 to 1.
- Patients may have previously failed non-platinum containing therapy or may never have previously progressed on treatment.
- Patients must be on treatment with platinum-based (cisplatin, oxaliplatin or carboplatin) treatment for locally advanced or metastatic pancreatic cancer and have received a minimum of 16 weeks of therapy without evidence of disease progression based on the investigator's opinion.
 - Discontinuation of the platinum component of the regimen for chemotherapy-related toxicity is permissible provided the patient has previously received at least 16 weeks of platinum-based therapy without evidence of disease progression ≤ 8 weeks after treatment with the platinum agent

Patients may have received <16 weeks of platinum therapy if platinum was not able to be used for medical reasons or was medically required to be discontinued for legitimate reason in the opinion of the investigator (ie allergy, intolerable organ dysfunction)

- Documented deleterious BRCA1/2 or PALB2 mutation (germline or somatic) as assessed by CLIA certified laboratory. Variants that are considered to be non-detrimental ("Variants of uncertain significance", "Variants of unknown significance", "Variant, favor polymorphism" or "benign polymorphism" etc) are not sufficient for study entry.
- Measurable disease is not required for enrollment.
- Adequate organ function confirmed by the following laboratory values obtained ≤ 7 days prior to the first day of rucaparib:
 - (1) Absolute neutrophil count (ANC) $\geq 1.0 \times 10^9/L$
 - (2) Platelets $>100 \times 10^9/L$
 - (3) Hemoglobin $\geq 9g/dL$
 - (4) Aspartate aminotransferase (AST) and alanine aminotransferase (ALT) $\leq 3 \times$ upper limit of normal (ULN)
 - (5) Total bilirubin $\leq 1.5 \times$ ULN; if liver metastases or metabolic disorder such as Gilbert's syndrome, then $\leq 2.5 \times$ ULN.
 - (6) Serum creatinine $\leq 1.5 \times$ ULN or estimated glomerular filtration rate (GFR) ≥ 45 mL/min using Cockcroft Gault formula.

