4.2 Exclusion Criteria

Patients will be excluded from participation if any of the following criteria apply:

CONFIDENTIAL

- Prior treatment with a PARP inhibitor
- Patients who have demonstrated resistance to platinum agents (e.g. oxaliplatin, cisplatin) are not eligible to participate in this study
- Clinical evidence of uncontrolled malabsorption and/or any other gastrointestinal disorder or defect that would, in the opinion of the investigator, interfere with the absorption of rucaparib
- Acute infection requiring intravenous antibiotics, antiviral or antifungal agents during the 14 days prior to first dose of rucaparib
- Symptomatic or untreated CNS metastases.
- Expected life expectancy of <12 weeks as determined by the investigator.
- For fertile patient (female able to become pregnant or male able to father a child), refusal to use effective contraception during the period of the trial and for 6 months after the last dose of rucaparib for female patients and 3 months for partners of male patients.
- Received any systemic treatment for pancreatic cancer ≤14 days prior to first dose of rucaparib.
- Non-study related minor surgical procedure ≤5 days, or major surgical procedure ≤21 days, prior to the first dose of rucaparib; in all cases, patients must be sufficiently recovered and stable before treatment administration.
- Active drug or alcohol use or dependence that would interfere with study compliance.
- Presence of any other condition that may increase the risk associated with study participation or may interfere with the interpretation of study results, and, in the opinion of the investigator, would make the patient inappropriate for entry into the study.

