6.2 Screening Phase

Following written informed consent, and unless otherwise specified, the following assessments will be performed during the 28 day period prior to the first dose of rucaparib. Assessments performed within this window, but prior to patient signing informed consent, are acceptable only if confirmed to have been standard of care.

Alterations to re-consenting patients:

In cases where a face-to-face scenario is not deemed practical or safe for re-consenting subjects, the study team will send the Informed Consent Form to patients in a way that is practical and convenient (e.g., email/scan or fax). In place of the face-to-face scenario, the appropriate delegated study personnel will explain the changes to the Informed Consent Form by way of a telephone call with the patient. After the re-consent discussion, the participant will be asked to sign the form and return a copy to the study team in a way that is practical and convenient (e.g., email/scan or fax). The Informed Consent Form copy will be signed by the appropriate study team personnel obtaining re-consent and filed in the designated investigator site file location. In addition to a wet ink signature, this process will be documented in the Electronic Medical Record (EMR).

Demographic information (birth date, race, gender, etc), including smoking status.

- Medical/oncology history, including date of cancer diagnosis, prior treatments and any surgical procedures
- Physical examination of body system, height and weight
- ECOG performance status (Appendix A)
- Vital signs (blood pressure, pulse, and temperature)
- Prior and concomitant medications and any surgical procedure
- 12-lead ECG
- Hematology (hemoglobin, hematocrit, WBC and differential [with ANC], and platelet count) ≤7 days prior to first dose of rucaparib.
- Serum chemistry (total protein, albumin, creatinine or estimated GFR using Cockcroft Gault formula, BUN, total bilirubin, ALP, ALT, AST, glucose, sodium, potassium, chloride, CO₂, calcium and phosphorous) ≤7 days prior to the first dose of rucaparib.
- Serum pregnancy test for women of childbearing potential (≤3 days prior to the first dose of rucaparib)
- Urinalysis performed on freshly voided clean sample (dipstick for protein, glucose, blood, pH and ketones). If dipstick findings are abnormal based on investigator judgment, then a microscopic evaluation will be performed to assess the abnormal findings.

CONFIDENTIAL

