7.8 Efficacy Evaluations

7.8.1 Tumor Assessments

Tumor assessments will be performed at Screening and within 7 days prior to the start of every odd numbered cycle (i.e., prior to the start of Cycles 3, 5, 7, etc.), until C11 and then every 12 weeks, and at the End of Treatment visit. If a CT scan was not performed at the End of Treatment visit, a CT scan should be performed at the 28-day Follow-up visit. Tumor response will be interpreted using RECIST Version 1.1 (Appendix B).

Tumor assessments should consist of clinical examination and appropriate imaging techniques (CT scans of the chest, abdomen, and pelvis with appropriate slice thickness per RECIST); other studies (MRI, X-ray, PET, and ultrasound) may be performed if required. If a patient has known brain metastases, this disease should be evaluated at each required assessment. The same methods used to detect lesions at baseline are to be used to follow the same lesions throughout the clinical study. Investigators should perform scans of the anatomical sites that, in their judgment, are appropriate to assess based on each patient's tumor status.

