Lesions that meet the criteria for radiographically defined simple cysts should not be considered as malignant lesions (neither measurable nor nonmeasurable) because they are, by definition, simple cysts.

Cystic lesions thought to represent cystic metastases can be considered as measurable lesions if they meet the definition of measurability described above. However, if noncystic lesions are present in the same patient, these are preferred as target lesions.

Lesions with Prior Local Treatment

Tumor lesions situated in a previous irradiated area or in an area subjected to other locoregional therapy are usually not considered measurable unless there has been demonstrated progression in the lesion.

Target Lesions

All measurable lesions up to a maximum of two lesions per organ and five lesions in total, representative of all involved organs, should be identified as target lesions and recorded and measured at baseline. Target lesions should be selected on the basis of their size (lesions with the longest diameter) and their suitability for accurate repeated measurements (either by imaging techniques or clinically). A sum of the longest diameter (LD) for all target lesions will be calculated and reported as the baseline sum LD. The baseline sum LD will be used as reference by which to characterize the objective tumor response.

Nontarget Lesions

RECIST criteria require unequivocal quantification of the changes in tumor size for adequate interpretation of the sum of target lesions. Consequently, when the boundaries of the primary are difficult to delineate, this tumor should not be considered a target lesion.

Guidelines for Evaluation of Measurable Disease

The same method of assessment and the same technique should be used to characterize each identified and reported lesion at baseline and during follow-up. Imaging-based evaluation is preferred to evaluation by clinical examination when both methods have been used to assess the antitumor effect of a treatment.

Evaluation of Target Lesions

Complete Response	Disappearance of all target lesions. Any pathological lymph nodes (whether target or nontarget) must have reduction in short axis to <10mm
Partial Response	At least a 30% decrease in the sum of the LD of target lesions, taking as reference the baseline sum LD.
Stable Disease	Neither sufficient shrinkage to qualify for PR nor sufficient increase to qualify for PD, taking as a reference the smallest sum LD since the treatment started.

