Progressive Disease	At least a 20% increase in the sum of all the LD of target lesions, taking as reference the smallest sum on study (this includes the baseline sum if that is the smallest on study). In addition to the relative increase of 20%, the sum must also demonstrate an absolute increase of at least 5mm. The appearance of one or more new lesions is also considered progression.

Evaluation of Nontarget Lesions

Complete Response	Disappearance of all nontarget lesions and normalization of tumor marker levels.
Stable Disease/Incomplete Response	Persistence of one or more nontarget lesion(s) or/and maintenance of tumor marker level above the normal limits.

CONFIDENTIAL

Progressive Disease	Appearance of one or more lesions and/or unequivocal progression of existing nontarget lesions.
----------------------------	---

If tumor markers are initially above the institutional ULN, they must normalize for a patient to be considered to be a complete responder.

Evaluation of Best Overall Response

The best overall response is the best response recorded from the start of the treatment until disease progression/recurrence (taking as reference for PD the smallest measurements recorded since the treatment started). The patient's best response assignment will depend on the achievement of both measurement and confirmation criteria.

Evaluation of Best Overall Response			
Target Lesions	Nontarget Lesions	New Lesions	Overall Response
CR	CR	No	CR
CR	Non-CR/Non-PD	No	PR
CR	Not evaluated	No	PR
PR	Non-PD or not evaluated	No	PR
SD	Non-PD or not evaluated	No	SD
Not Evaluated	Non-PD	No	NE
PD	Any	Yes or No	PD
Any	PD	Yes or No	PD
Any	Any	Yes	PD
NE = not evaluable			

Patients with global deterioration of health status requiring discontinuation of treatment without objective evidence of disease progression at that time should be classified as having symptomatic deterioration. Every effort should be made to document the objective progression, even after discontinuation of treatment.

In some circumstances, it may be difficult to distinguish residual disease from normal tissue. When evaluation of CR depends on this determination, it is recommended that the residual lesion be investigated (fine needle aspiration/biopsy) prior to confirming the complete response status.

Confirmatory Measurement/Duration of Response

Confirmation

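### Chemotherapy may be given after the baseline scan, so its effect can count toward a rucaparib response and can hide early regrowth

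*Combined protocol and SAP*

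**What the plan says.** **Scan window.** Section 3.1.1 states: "All patients will undergo screening assessments within 28 days prior to the first dose of rucaparib". Imaging is among those assessments, and the Schedule of Assessments (6.1) gives it the Day -28 to Day -1 column. Hematology and chemistry are held to 7 days and the pregnancy test to 3 days. The tumor scan has no tighter limit in 6.1 (footnote m), 6.2 or 7.8.1. Section 7.8.1 says only: "Tumor assessments will be performed at Screening and within 7 days prior to the start of every odd numbered cycle".

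**Scans before consent.** Section 6.2 adds: "Assessments performed within this window, but prior to patient signing informed consent, are acceptable only if confirmed to have been standard of care". A routine restaging scan taken during chemotherapy can therefore be the baseline.

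**Chemotherapy.** Section 4.1 recruits from active treatment: "Patients must be on treatment with platinum-based (cisplatin, oxaliplatin or carboplatin) treatment for locally advanced or metastatic pancreatic cancer". It also admits patients whose platinum component has been stopped. Section 4.2 excludes a patient who "Received any systemic treatment for pancreatic cancer ≤14 days prior to first dose of rucaparib".

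**Reference for response and progression.** Appendix B says of the baseline measurement: "The baseline sum LD will be used as reference by which to characterize the objective tumor response". Partial response is "At least a 30% decrease in the sum of the LD of target lesions, taking as reference the baseline sum LD". Progression needs a 20% rise (and at least 5 mm), "taking as reference the smallest sum on study (this includes the baseline sum if that is the smallest on study".

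**Analysis.** Section 8.4 estimates ORR with a 95% confidence interval. It sets no ORR hypothesis and no sensitivity analysis for treatment given after the baseline scan.

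**The concern.** The baseline sum is meant to describe the tumor as rucaparib starts. Under these two windows it can instead describe the tumor before one more chemotherapy dose. Patients enter because they have not progressed on platinum-based treatment, and section 1.1 describes typically durable, good responses to platinum in mutation carriers. Some shrinkage between scan and day 1 is therefore plausible.

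Two things are at stake. First, such shrinkage counts toward the 30% fall and can turn a smaller change on rucaparib into a recorded response. With one arm, no control group carries the same error. Second, if the tumor is smaller on day 1 than at baseline, growth back to the baseline size reads as no change. That can delay a call of progression and so may reach the primary endpoint.

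**Working it through.** **1. The plan's own figure.** ORR and duration of response (DOR) have no stated power. The only efficacy power is 81% for PFS6, 44% against 60%, with 42 patients, two-sided 5%, exponential survival, 42 months of accrual and 6 of follow-up (8.4). Check on the log-hazard scale:
- Hazard ratio = ln(0.60)/ln(0.44) = 0.622.
- Event probability under the alternative = 0.837, so 42 × 0.837 = 35.1 events.
- Power = Φ(√35.1 × |ln 0.622| − 1.96) = 80.3%, close to the stated 81%.

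This point does not alter that figure or the sample size.

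**2. The gap.** Earliest scan: 28 days before first dose. Latest permitted chemotherapy: 15 days before. 28 − 15 = 13 days in which a dose may follow the scan. This is an interval in which a dose can fall, not 13 days of exposure.

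**3. Span of the first response comparison.** Cycle 3 Day 1 is study day 57, which is 56 days after day 1. From a day -28 scan to that day is 28 + 56 = 84 days, or 77 if the scan is done 7 days earlier. Of the 84 days, 28 (33%) precede rucaparib.

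**4. Effect on partial response.** Let s be the fractional shrinkage between scan and day 1. The documents give no value, so s is assumed. Further shrinkage needed from day 1 = 1 − 0.70/(1 − s).

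| s (assumed) | further shrinkage needed |
|---|---|
| 0% | 30.0% |
| 5% | 26.3% |
| 10% | 22.2% |
| 15% | 17.6% |
| 20% | 12.5% |
| 25% | 6.7% |

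**5. Effect on ORR.** Measurable disease is not required (4.1), so the denominator is at most 42 and is otherwise unknown. One miscredited response adds 1/42 = 2.4, 1/30 = 3.3 or 1/20 = 5.0 points (denominators assumed).

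**6. Effect on progression.** Take a baseline sum of 100 mm, an unmeasured 80 mm on day 1, and 100 mm at the Cycle 3 scan. Growth on rucaparib is 100/80 − 1 = 25%, above the 20% threshold and 20 mm in absolute terms. The recorded change from the smallest measured sum is 0%, so the scan reads as stable disease. At that scan, progression would need 120 mm, which is 120/80 − 1 = 50% above the day 1 size.

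**The case against.** **Permitted is not the same as frequent.** The documents do not say how many patients are dosed after their scan, or how much tumors still shrink at that stage. Entry generally requires at least 16 weeks of therapy without progression, and lack of progression is not continuing shrinkage. This stands: the problem is shown to be possible, and its size is not shown.

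**Confirmation gives some protection.** A response should be confirmed at least 4 weeks later. With a first scan in the 7 days before Cycle 3 that means about weeks 11 to 12, some 13 to 14 weeks after a dose on day -15. Section 1.1 also says that 92% of patients taken off chemotherapy progress or recur within 6 months, so a fall due to chemotherapy alone is less likely to last. But the confirmatory scan uses the same baseline, so the head start remains.

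**The error can run the other way.** A tumor may grow between an old scan and day 1. With 10% growth, the fall needed from day 1 is 1 − 0.70/1.10 = 36.4%, so response becomes harder to reach. The upward push on ORR applies to patients whose tumors shrink after the scan; the net direction over all patients is not known.

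**Stronger readings that the documents do not support.**
- A reader might infer that ORR will be judged against the 16% seen in the earlier rucaparib trial in pancreatic cancer. That figure is background in section 1.1. Section 8.4 only estimates ORR, and the one planned historical comparison is PFS6 against 44%.
- A reader might infer that DOR is inflated too. DOR starts at the first documented response on study, and progression is taken from the smallest sum. Carry-over changes who counts as a responder and when, but the direction for DOR is not fixed.
- A reader might attribute the carry-over to platinum specifically. The exclusion covers any systemic treatment, and platinum may already have stopped.

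**Conclusion.** The gap holds on the text. A chemotherapy dose can follow the reference scan by up to 13 days, and no rule or analysis deals with it. Where tumors shrink as a result, ORR is inflated: under an assumed 10% or 20% shrinkage, the fall needed on rucaparib drops from 30% to 22.2% or 12.5%, and each miscredited response is worth 2.4 to 5.0 points for an assumed 42 to 20 patients with measurable disease.

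PFS6 may also be affected, but less directly. Scans are due before Cycles 3, 5 and 7 (days 57, 113 and 169), so regrowth missed at the first can still be caught by month 6. Only a call of progression that slips past month 6 changes the estimate.

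No formal test of ORR is affected, because none is planned. The point deserves a change because the remedy is cheap, not because a large bias has been shown.

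**What to change.** **Scan timing.** In section 6.2 and the Schedule of Assessments, state that a screening CT not already done as standard of care is taken after the last dose of prior systemic therapy. The existing treatment-free interval leaves 14 days for it. That interval and the dosing stay as they are.

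**Earlier standard-of-care scans.** Keep accepting them without a repeat CT. Flag every patient who received systemic therapy after the baseline scan. Footnote c of the schedule already requires prior-treatment dates in the medical record, so only those and the scan date are needed. This also works for patients already enrolled.

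**Analysis.** In section 8.4.2, pre-specify ORR with and without flagged patients, with DOR and PFS6 shown the same way as supportive results. The flag is fixed before the first rucaparib dose, so the split does not select on outcome. Flagged and unflagged patients may still differ in other ways, so a difference between the results is not purely carry-over.

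**Cost.** One sensitivity table, wider intervals in the reduced set, and some constraint on when the CT is booked. Delayed effects of earlier chemotherapy remain: a scan the day after the last dose would comply and still precede most of that dose's effect.

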4.3 Patients or Partners of Patients with Reproductive Potential

Pregnancy is an exclusion criterion for study patients. Female study patients of childbearing potential, must not be considering getting pregnant during the study until 6 months following the last dose of rucaparib. Female partners of childbearing potential of study patients must not be considering getting pregnant during the study until 3 months following the last dose of rucaparib.

A woman is considered to be of childbearing potential unless 1 of the following applies:

- She is considered to be permanently sterile. Permanent sterilization methods include hysterectomy, bilateral salpingectomy, and bilateral oophorectomy.
- She is postmenopausal, defined as no menses for 12 months without an alternative medical cause. A high follicle-stimulating hormone (FSH) level consistently in the postmenopausal range (30 mIU/mL or higher) may be used to confirm a postmenopausal state in women not using hormonal contraception or hormonal replacement therapy; however, in the absence of 12 months of amenorrhea, a single FSH measurement is insufficient to confirm a postmenopausal state.

Female patients of childbearing potential must have a negative serum pregnancy test result less than 3 days prior to administration of the first dose of rucaparib. In addition, a serum pregnancy test must be performed < 3 days prior to Day 1 of every cycle from Cycle 2 and beyond. Treatment should be discontinued immediately in any woman found to have a positive pregnancy test while taking rucaparib. A serum pregnancy test will also be performed at the End-of-Treatment Visit.

Female study patients of reproductive potential must practice total abstinence or use a highly effective method of contraception (failure rate < 1% per year) during treatment and for 6 months following the last dose of rucaparib. Female partners of reproductive potential and their male partners must practice total abstinence or use a highly effective method of contraception (failure rate < 1% per year) during treatment and for 3 months following the last dose of rucaparib. The following are allowable only:

- Ongoing use of progesterone-only injectable or implantable contraceptives (e.g., Depo Provera, Implanon, Nexplanon)

CONFIDENTIAL

This material is the property of the University of Pennsylvania.

- Placement of an intrauterine device or intrauterine system
- Bilateral tubal occlusion
- Male sterilization, with appropriate post-vasectomy documentation of absence of sperm in ejaculate
- True, complete (as opposed to periodic) abstinence.

Patients will be instructed to notify the investigator if pregnancy (own or female partner's) is discovered either during or within 6 months of completing treatment with rucaparib.

